been proven to reduce hospital admissions in patients with SCD. Hydroxycarbamide induces fetal hemoglobin production (HbF) thereby decreasing sickle hemoglobin erythrocyte polymers, haemolysis, and painful vaso-occlusive crisis. Rigorous investigation over the past 30 years has demonstrated the efficacy of hydroxycarbamide in reducing disease complications, health care utilization, and costs for patients with SCD. However, compliance rates are well established to be low and linked to a variety of reasons including fear of side effects, stigma and low health literacy. Although there are no prospective studies that evaluate the efficacy of hydroxycarbamide on reducing the incidence of SCR, large retrospective studies have highlighted the protective effect of hydroxycarbamide on SCR and maculopathy. These studies suggest hydroxycarbamide, by elevating levels of HbF, can significantly reduce the odds of developing SCR and reduce the progression of sickle maculopathy. There is also emerging evidence that the severity of SCR and maculopathy correlates with severity of systemic anaemia associated with SCD. As such, retinal screening may improve compliance with hydroxycarbamide if evidence confirming protective retinal effects are corroborated. Retinal screening may also highlight the need for escalations of management to the haematologist.

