#### Secondary outcomes

- 1. The prevalence of each stage of SCR and presence of maculopathy by age and genotype
- 2. The correlation of each stage of SCR and maculopathy to severity of SCD as determined by number of hospital admissions in the preceding 12 months/serum HbF/ serum Hb.
- 3. The impact of SCR and presence of maculopathy on vision-related quality of life.
- 4. The acceptability to patients of routine retinal imaging for SCR and maculopathy
- 5. The development of updated consensus definitions and a modernized classification system for SCR and maculopathy, leveraging the increased insight into retinal tissue anatomy and vascular blood flow afforded by contemporary imaging technologies

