The research team will also complete an electronic case report form recording basic demographic history such as: Year of birth, Sex, Sickle genotype, Number of hospital admissions with acute sickle crisis, medical history, current medications and interventions for SCD, previous history of stage 4 or 5 sickle cell retinopathy, ocular comorbidities, previous ocular interventions and most recent serum haemoglobin (Hb) and serum haemoglobin F (HbF) within 3 months of study entry.

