#### 5.1 Data Analysis plan

The primary analysis is to estimate the prevalence of SCD-related vision loss. In addition to the calculated value, a corresponding 95% confidence interval will be obtained to illustrate its associated uncertainty. We will also calculate prevalence of each stage of SCR and maculopathy by age bracket and genotype. The unit of analysis will be the eye with the worse SCR stage, or randomly chosen eye if both are of the same stage. The chi-square test for trend will be used if groups are ordinal. The Kruskal-Wallis test (categorical factors) or Spearman rank (ordinal factors) will be used when comparing SCR stage between groups, as above.

The association between SCD severity (as assessed by number of hospital admissions in past year and haemoglobin and haemoglobin F level within 3 months) with SCR stage and presence of sickle maculopathy will be examined using Spearman Rank or Pearson product correlation. Multivariable analysis such as logistic regression will be undertaken to assess the simultaneous effects of multiple factors on stage of SCR and presence of maculopathy. The correlation between NEI VFQ-25 global score and acceptability with best

corrected visual acuity, SCR stage and presence of maculopathy will also be assessed using Spearman rank correlation.

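### Hb and HbF are chosen by date alone, so crisis or post-transfusion values can stand in for chronic severity in secondary outcome 2

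*Protocol*

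**What the plan says.** Section 3.1 lists the items the research team enters for each participant, among them the "most recent serum haemoglobin (Hb) and serum haemoglobin F (HbF) within 3 months of study entry". Section 5.1 carries the window into the analysis: severity is "as assessed by number of hospital admissions in past year and haemoglobin and haemoglobin F level within 3 months", and its association with retinopathy stage and maculopathy "will be examined using Spearman Rank or Pearson product correlation". The second secondary outcome in section 2.1 relates stage and maculopathy to "severity of SCD as determined by number of hospital admissions in the preceding 12 months/serum HbF/ serum Hb". The rationale in section 1.3 cites evidence that "the severity of SCR and maculopathy correlates with severity of systemic anaemia associated with SCD", and describes HbF raised by long-term treatment as protective.

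The activity table in section 3.5.3 has no study blood draw, so the values come from routine care. The eligibility criteria in section 3.4 do not exclude a recent crisis or transfusion. No section asks for a steady-state sample or sets an interval after an acute episode or transfusion. The nearest safeguards are an item for "current medications and interventions for SCD" in section 3.1 and, in section 5.1, the sentence "Multivariable analysis such as logistic regression will be undertaken to assess the simultaneous effects of multiple factors on stage of SCR", which names no covariates.

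**The concern.** Retinal stage is described in section 1.1 as progressive, and the exposures of interest are a patient's usual Hb and HbF. The rule selects on recency only. I take it as general clinical understanding, not stated in the protocol, that Hb falls from its usual level in a crisis, and that transfusion raises Hb and dilutes HbF. For such patients the recorded value describes a temporary state. Because the rule asks for the latest value, a site that holds a steady-state result from earlier in the window has no licence to use it.

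Three consequences follow for secondary outcome 2:

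- Added noise weakens the correlation with stage.
- If recent crisis or transfusion is more common at some stages than others, the error is differential and can bias the correlation.
- Frequently admitted patients are the likeliest to have an acute latest value, so Hb and HbF partly echo the admissions count. This blurs their separate effects if all three enter the multivariable model.

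This is a rule about what is collected. A later analysis plan cannot restore a steady-state value or a sample date that was never recorded.

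**Working it through.** **Plan's own figures.** For p = 0.10 and a half-width of 0.025, n = 1.96² × 0.1 × 0.9 / 0.025² = 553.2, so 554 reproduces. The three-standard-error rule in section 5 corresponds to r = 3/√553 = 0.128. The 95% half-width for a correlation at n = 554 is about 1.96/√551 = 0.083. None of these changes, because the point concerns a measurement definition.

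**Inputs not in the protocol (assumptions).** Crisis admissions average 1.5 a year and are overdispersed (gamma-Poisson, k = 0.5 to 2). Steady-state Hb has SD 15 g/L. An acute value is 10 or 20 g/L lower. The true Hb-stage correlation is 0.18 in absolute size.

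**Step 1: share with an admission in three months.** The mean in the window is 1.5/4 = 0.375. The share is 1 − (1 + 0.375/k)^(−k), which gives 24%, 27% and 29% for k = 0.5, 1 and 2. This is an upper limit on the share f whose latest value is acute, because a patient admitted ten weeks ago may have had a later clinic sample, which the rule would select. Transfusion outside an admission is not counted.

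**Step 2: attenuation when the shift is unrelated to stage.** With d the shift in SD units, observed r = true r / √(1 + f(1 − f)d²). Starting from 0.18:

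| Share of admitted patients whose latest value is acute | f (from 27%) | 10 g/L (d = 0.67) | 20 g/L (d = 1.33) |
|---|---|---|---|
| All | 0.27 | 0.173 | 0.155 |
| Half | 0.135 | 0.176 | 0.164 |
| A quarter | 0.0675 | 0.178 | 0.171 |

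Worked example, top right: 1 + 0.27 × 0.73 × 1.78 = 1.35, and 0.18/√1.35 = 0.155. The largest loss is about 0.025, well inside the half-width of 0.083.

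**Step 3: the same in SD units, for Hb or HbF.** Take r = 0.14 (power 91% at n = 554 by Fisher z). A 1 SD shift in 5% to 30% of values gives r = 0.137 to 0.127 and power 90% to 85%. A harsher assumption is that such values carry no information about the usual level. Then r = 0.14(1 − f) = 0.133 to 0.098, with power 88% to 64%. I treat this as an outer bound, since a shifted value still contains the patient's own level.

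**Step 4: bias when the share differs by stage.** Suppose the true correlation is zero, 30% of patients have advanced stage, and the shift is 1 SD. The expected correlation is about (f₁ − f₀)√(0.3 × 0.7)/√(1 + f̄(1 − f̄)).

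- Shares of 10% (early) and 20% (advanced): f̄ = 0.13, giving 0.1 × 0.458/1.055 = 0.043. The simulated Spearman value is about 0.04, with rejection in about 15% of studies.
- Shares of 10% and 30%: f̄ = 0.16, giving 0.2 × 0.458/1.065 = 0.086. The simulated Spearman value is about 0.08, with rejection in about 49%.

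The sign follows the shift: a crisis fall and a post-transfusion rise in Hb push in opposite directions.

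**The case against.** The strongest reply is that the damage is small and partly guarded against. Patients are mainly approached in haematology clinic (sections 3.2 and 3.3), where a routine sample may well be the latest one, and no inpatient recruitment is described. The planned correlation loses only a few hundredths even in the worst shift case above. Section 5.1 also plans a multivariable analysis, whose covariates and sensitivity analyses can properly be left to an analysis plan that is not shown. All of this stands as an argument about size. It does not alter the selection rule.

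Two stronger readings are tempting. A reader might infer that Hb and HbF become largely a second measure of admissions, or that the severity-retinopathy results are seriously distorted. The protocol supports neither: it gives no frequency or size for acute values, and a correlation between Hb and admissions is not itself a planned result. A reader might also infer that the case report form omits the sample date and clinical state. The form is not shown, and section 3.1 gives its items as examples, so this cannot be asserted. What can be said is that the protocol names no such item. The item on current interventions may identify regular transfusion, but it is not tied to the sample and would not reveal a one-off transfusion or a crisis on the day.

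A further fair objection concerns the remedy. Excluding recently admitted or transfused patients outright would make missingness depend on severity, in a study that seeks a representative sample. That is accepted in the fix.

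**Conclusion.** The point holds as a weakness in a measurement rule. Sections 3.1 and 5.1 select Hb and HbF by date alone, while section 2.1 and the rationale use them as markers of chronic severity. The likely effect on the Hb and HbF correlations with stage is modest attenuation, illustratively from 0.18 to between about 0.15 and 0.18. If recent crisis or transfusion is related to stage, bias in either direction is possible, of the order of 0.04 to 0.08 under the assumptions shown. Some dependence between Hb or HbF and admissions is also built into any model that includes both. These sizes rest on assumed admission rates, shifts and SDs, so the true distortion is unknown. The consequence is confined to secondary outcome 2 and models using Hb or HbF. The primary prevalence estimate and its sample size are untouched. It is worth correcting because it is cheap now and cannot be repaired after data collection.

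**What to change.** In sections 3.1 and 5.1, ask for the most recent steady-state Hb and HbF within the three-month window where one exists, and otherwise the most recent value. The investigators should define steady state, including any interval after an acute episode or transfusion.

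Name two items for the case report form: the sample date, and a yes/no flag for acute admission or transfusion shortly before the sample. Keep all participants with a value in the main correlations. Repeat the Hb and HbF analyses without flagged values as a sensitivity analysis.

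The cost is two fields taken from existing records, with no new blood test. Some values will be slightly older. The sensitivity subset will under-represent frequently admitted and regularly transfused patients, so it should be read beside the main result and not replace it.

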#### 3.2 Participants and recruitment

Haematology teams in participating sites will inform consecutive patients with SCD ≥ 16 years about the study and refer to the ophthalmology unit for routine retinal screening. In units where patients have already been referred for screening but are awaiting appointments in the ophthalmology department can also be recruited in the ophthalmology department. In the ophthalmology department, patients with SCD who meet the study inclusion criteria will be invited by the clinical team to take part. Participating Trusts have been selected as they already offer or are willing to offer routine eye screening for SCD patients as part of standard of care and confirmed to have ultra-widefield fundus imaging and spectral domain OCT.

We have used the 2021 national haemoglobinopathy registry (NHR) report to identify centres treating patients with SCD in England. Eligible centres had to meet the following criteria:

- 1. At least 60 patients with SCD on the registry
- 2. Ultra-wide field fundus photography
- 3. Spectral domain OCT imaging
- 4. A routine screening programme for SCR in place or willing to institute one
- 5. Capacity and willingness to participate in the present study

#### 3.3 Recruitment and Consent

600 individuals who have been diagnosed at any point with SCD will be identified from up to 16 geographically dispersed participating NHS Trusts across the UK.

Individuals identified to be eligible will be approached in clinic by their consultant haematologist or a member of their clinical team, who will explain the background, aims and nature of the project, and provide further information about the project in an accessible format (participant information sheet; PIS). Potential participants can also be identified from the ophthalmology waiting list if they have been referred as part of a routine screening programme from haematology. An invitation letter informing potential participants due to attend a sickle cell clinic can be sent out with appointment letters so that they are aware of the study before attending the clinic.

Interested participants will be invited to attend the eye clinic where they will be consented and research activities will occur. For those who do not speak English or would benefit from translation services, this will be funded by the study. Informed consent can also be obtained over the telephone. Potentially eligible participants who have previously given consent to contact for any research can be approached by the research team by telephone and if willing to consider participating, the PIS can be posted to them. There will be an opportunity to discuss the study before consent is obtained in the eye clinic or by telephone, and it will be made clear that the individual is free to withdraw from the study at any point.

#### Telephone consent

Participants can provide consent verbally to a member of the research team over the telephone. Before taking consent the member of the local research team will ensure that they have a witness present who can verify that informed consent was taken. The member of the local study team acting as a witness does not need to be named on the Delegation Log. The member of the local research team who is taking remote consent will read each of the statements on the ICF to the potential participant and will insert their initials in each of the associated boxes to confirm that the participant agrees with the statement. After consent has been taken the witness will

countersign the informed consent form (ICF) and a copy of the completed form sent to the participant. The method by which this was done will be recorded at the end of the consent form. A copy of the ICF will be placed in the participant's notes which will record the name of the person taking the consent, the witness, and the date this was done. Oral confirmation of ongoing consent to participate in the Sickle Eye Project should be sought from the participant when they present for their procedure, and this should be recorded in the participant's medical notes

# 3.4 Eligibility criteria:

#### Inclusion criteria

- Willingness to participate
- · Ability to provide informed consent
- Age 16 years or older
- Diagnosis of SCD of any genotype

#### Exclusion criteria

- Inability to consent
- Poor image quality
- Age <16 years

- Sickle cell trait only

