# 1. Introduction

# 1.1 Proliferative sickle cell retinopathy

Sickle-cell disease (SCD) is one of the most common genetic disorders in the UK, with approximately 15000 people affected. It is a debilitating, multisystem disease, associated with episodes of acute illness, progressive organ damage and reduced life expectancy. There are 13 genetic variants of SCD, with HbSS genotype being most common (>70%) and most severe, followed by HbSC genotype. SCD affects predominantly people of African and Afro-Caribbean descent and evidence demonstrates inequalities in healthcare outcomes and access for people with SCD . An all-party parliamentary group inquiry reported low awareness of SCD and its complications among healthcare professionals and underinvestment in sickle cell research.

Proliferative sickle cell retinopathy (SCR) is the most common ophthalmic manifestation of SCD and can result in significant sight loss, although the prevalence in the U.K is not currently known. Decades old retrospective and cohort studies from other countries have estimated prevalence of SCR in SCD patients at up to 48% and associated with significant sight loss in up to 12%. Importantly, life expectancy for SCD has increased from 14 years in 1973 to >60 years in high-income countries with improvement in management and healthcare delivery. Evidence from cohort studies and large retrospective studies demonstrate increasing incidence of SCR with age. As such, we could expect the prevalence of SCR and potentially associated visual impairment, to be currently higher in the UK than previously reported.

Five stages of SCR were described by Goldberg in 1971. These are progressive with stages 1-3 being asymptomatic, stage 3 reflecting the presence of retinal neovascularisation in the far periphery known as seafan neovascularisation, vitreous haemorrhage (bleeding inside the eye) develops in stage 4 and rhegmatogenous and/or tractional retinal detachment in stage 5.

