### Fidelity check demonstrating adherence to image acquisition protocol

Green: Adherence to image acquisition protocol in ≥90% of cases.

Amber: Adherence to image acquisition protocol in ≥80%

Red: Adherence to image acquisition protocol in <80% of cases

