#### Main study primary outcome

1. The prevalence of visual impairment due to SCR or maculopathy (defined as best corrected visual acuity LogMAR ≥ 0.3 in at least one eye) in a representative sample of the UK population with SCD

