### 3. Overall study design

## 3.1 Study design

This is a cross-sectional, non-interventional study. Potential participants will be introduced to the study by their haematologist, who will also provide them with the participant information sheet. Identification of potential participants in the haematology clinic is important to prevent ascertainment bias and sample a representative

sample of people with SCD. All patients with SCD are offered regular specialist follow-up by a haematologist in the UK. The national haemoglobinopathy registry record for 2021 reported 12904 people with SCD confirming that an overwhelming proportion of SCD patients are under specialist care in the UK. Informed consent will be obtained from willing participants by the ophthalmology team either in the eye department or over the telephone. Informed consent will be obtained prior to the collection of any data. Once consented, participants will have best corrected visual acuity (BCVA) with habitual correction and pinhole measured, a slit lamp examination of the anterior segment and fundus, spectral-domain optical coherence tomography (SD-OCT), optical coherence tomography-angiography (OCT-A) and ultra-widefield fundus photography performed in the eye department. Subsequently, the participant will have the NEI VFQ-25 questionnaire and the acceptability of retinal screening questionnaire administered.

In some departments, it may be more appropriate for the haematology team to share brief details about the study, including the study leaflet with potential participants. Interested participants can be sent the participant information sheet ahead of their eye clinic appointment.

The NEI VFQ-25 questionnaire can be administered over the telephone either at the time of consent or after the visit to the eye department. The acceptability of retinal screening questionnaire has to be administered after the retinal imaging has been performed.

If the NEI VFQ-25 is completed over the telephone, this must be done ±28 days of the eye clinic visit for examination and retinal images.

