### 5. Statistics and data analysis

The primary analysis will be to calculate the prevalence of sickle cell retinopathy/maculopthy-related vision loss together with its 95% confidence interval (CI) to illustrate the uncertainty in the estimate. It is anticipated the prevalence will be approximately 10% based on data from Saidkasimova et al. With 554 subjects the prevalence can be estimated with a 95% confidence interval with a 5% width e.g. expected to be from 7.5% to 12.5%. The sample size (N) was chosen to satisfy this 5% width, given the confidence interval is expected to be p + 1.96\*sqrt(p\*(1-p)/n), where p=0.1. To obtain this number of evaluable subjects we estimate approximately 600 subjects will have to be enrolled, this allows for a drop-out rate of just under 10%.

A sample size of 600 will also allow accurate estimates of the stages of SCR and maculopathy occurrence to be obtained. For example, the following CIs are based on a French retrospective cohort of 942 patients:

	%	N	95%CI (23%-	width
Stage 0	30%	166	37%) (34%-	14%
Stage 1-2	40%	222	46%) (13%-	13%
Stage 3	20%	110	27%)	15%
Stage 4	5%	28	(8%-20%)	12%
Stage 5	5%	28	(8%-20%)	12%
	100%	554		

Other endpoints also include the calculation of the prevalence of each stage of SCR by age bracket and genotype. Sample size relevance in these circumstances can be illustrated by considering a hypothetical outcome. For example, under the null hypothesis there would be no association between prevalence and age, and given the hypothetical distributions of stage, and age below, it can be shown that the estimated correlation (Spearman Rank) has a greater than 3 SE difference (from zero) with 554 cases. This suggests powering is adequate for associations of this size, by the 'rule of three', for 85% power (Zbeta=1) and 5% sig level (Zalpha=1.96).

				Age Group					
				O. Guip					rate
N		3.1%	7.4%	8.2%	14.0%	16.9%	21.7%	9.7%	overall
	Stage/Age	16-25	 26-35	36-45	46-55	56-65	66+		
	5	1	5	6	6	5	2		
SCR	4	2	5	5	8	6	3		
	3	23	28	28	20	12	4		
	1-2	46	56	55	39	23	8		
	0	24	42	40	27	19	6		
	l	96	136	134	100	65	23	554	
		Spearm	an Rank -	0.14 (95%	CI:-0.23 t	o -0.06), p	o=0.001		

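### The undefined exclusion for poor image quality acts after enrolment and is likely related to the outcome, so it can bias the visual-impairment and stage 4/5 prevalences downward

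*Protocol*

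**What the plan says.** Section 3.4 of the protocol lists "Poor image quality" as an exclusion criterion. It does not say what counts as poor, whether one bad eye or one failed modality is enough, or what happens when the eye disease under study causes the poor image.

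The primary outcome in Section 2.1 is visual impairment due to SCR or maculopathy, "defined as best corrected visual acuity LogMAR ≥ 0.3 in at least one eye", to be estimated "in a representative sample of the UK population with SCD". Section 3.1 explains recruitment through haematology clinics as "important to prevent ascertainment bias and sample a representative" sample.

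On the disease, Section 1.1 says of the stages: "These are progressive with stages 1-3 being asymptomatic"; then "vitreous haemorrhage (bleeding inside the eye) develops in stage 4 and rhegmatogenous and/or tractional retinal detachment in stage 5".

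On timing, Section 3.1 places consent before any data collection, and imaging after consent. The activity table in Section 3.5.3 gives the eligibility check to the haematology team.

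On measurement, Section 3.5.3 takes acuity from a chart with habitual correction and pinhole. It also schedules slit-lamp and dilated examination for every participant, with vitreous haemorrhage among the findings to be documented.

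**The concern.** An eligibility criterion should be assessable before enrolment and should not depend on the outcome. This one fails the first test, since nobody can judge an image that has not yet been taken. It probably fails the second as well. Blood in the vitreous lowers acuity and obscures a fundus image, and a detachment may do both. If impaired participants are excluded at a higher rate than unimpaired ones, the numerator shrinks faster than the denominator and the estimated prevalence falls.

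The headline estimate and the stage 4 and 5 prevalences are at stake. A representative recruitment route does not help if the sample is filtered afterwards on something linked to the outcome. Nothing elsewhere in the protocol keeps participants with ungradable images in the denominator or reports them as their own category.

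**Working it through.** **1. The plan's own figure.** Section 5 assumes p = 0.10 and a 95% interval 5 points wide.

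n = 1.96² × 0.10 × 0.90 / 0.025² = 553.2, rounded up to 554. At n = 554 the interval is 7.5% to 12.5%. The planned figure reproduces, and the half-width to compare any bias against is 2.5 points.

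**2. Direction.** Let f be the share of impaired participants excluded for poor images and g the share of unimpaired participants excluded.

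Expected estimate = p(1−f) / [p(1−f) + (1−p)(1−g)]

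This is below p exactly when f > g. The protocol gives neither f nor g. The reasons to expect f > g are its own statements: stages 1-3 are asymptomatic, stage 4 is vitreous haemorrhage, stage 5 is detachment, and acuity was preserved in most maculopathy patients in the single-centre study cited in Section 1.2.

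**3. How the plan's illustration links stage to vision loss.** In the hypothetical age table in Section 5, the rate row equals (stage 4 + stage 5)/N in each age band: 3/96 = 3.1%, 10/136 = 7.4%, 11/134 = 8.2%, 14/100 = 14.0%, 11/65 = 16.9%, 5/23 = 21.7%. Overall it is 54/554 = 9.7%, close to the planned 10%. This is an illustration. The text does not state that all impairment lies in stages 4 and 5.

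**4. Illustrative size.** Assumptions: stages 4 and 5 are 5% each (Section 5 stage table) and carry all impairment. Excluded shares, which are not in the protocol, are u4 = 20-60% of stage 4, u5 = 10-30% of stage 5 and uo = 2-5% of others.

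Estimate = [0.05(1−u4) + 0.05(1−u5)] / {[0.05(1−u4) + 0.05(1−u5)] + 0.90(1−uo)}

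- Lowest (u4 = 0.6, u5 = 0.3, uo = 0.02): (0.020 + 0.035) / (0.055 + 0.882) = 0.055/0.937 = 5.9%.
- Highest (u4 = 0.2, u5 = 0.1, uo = 0.05): (0.040 + 0.045) / (0.085 + 0.855) = 0.085/0.940 = 9.0%.
- Stage 4 alone, true 5%: 0.020/0.937 = 2.1% to 0.040/0.940 = 4.3%.

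The bias in the primary estimate runs from 1.0 to 4.1 points.

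**5. When the interval misses the truth.** With 600 enrolled and a true 10%:

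- f = 20%, g = 0: 0.080/0.980 = 8.2% on 588 people, interval 5.9% to 10.4%, which still covers 10%.
- f = 25%, g = 0: 0.075/0.975 = 7.7% on 585 people, interval 5.5% to 9.9%, which does not.
- f = 30%, g = 5%: 0.070/0.925 = 7.6% on 555 people, interval 5.4% to 9.8%, which does not.

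**6. A milder case.** Suppose only 60% of impairment lies in active stage 4/5, split equally, and the other 40% is lost at the same rate as other participants.

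- Lowest: (0.03 × 0.4 + 0.03 × 0.7 + 0.04 × 0.98) / (0.0722 + 0.882) = 0.0722/0.9542 = 7.6%.
- Highest: (0.03 × 0.8 + 0.03 × 0.9 + 0.04 × 0.95) / (0.089 + 0.855) = 0.089/0.944 = 9.4%.

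The worst bias is then 2.4 points, just inside the planned half-width.

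**The case against.** **The size is assumed.** This stands. No ungradable rate appears in the protocol. Maculopathy also counts towards the outcome. Section 1.3 notes that vitrectomy clears the blood while acuity often stays poor, so some impaired eyes may have clear media and image well. If poor images arise mainly from unrelated causes such as cataract, the bias shrinks, and it reverses if g exceeds f.

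**The rule does not remove every affected eye.** A reader might infer that all eyes with haemorrhage or detachment are lost and that the estimate is certain to be too low. The text does not support that. Poor is undefined and some of these eyes can be imaged, so only a share is lost.

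**The rule may apply to single eyes.** The protocol does not say so, and the problem would remain. The outcome needs one impaired eye, and Section 5.1 analyses the eye with the worse stage, which is the one more likely to be dropped.

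**The analysis plan may deal with it.** That plan is not at hand. Eligibility is set in the protocol, however, and an analysis plan would not normally restore people whom the protocol excludes.

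**Images are needed to establish cause.** This stands in part. Acuity needs no image, but attribution to SCR or maculopathy often does. Section 1.2 links recognition of maculopathy to modern imaging, and Section 1.4 rates ultra-widefield photography above traditional examination. Dense blood can also block funduscopy. The remedy therefore needs a rule for undetermined cause.

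Two further inferences are tempting but unsupported. The pilot criterion, "Adherence to image acquisition protocol in ≥90% of cases", concerns how images are acquired. A fully adherent acquisition can still be ungradable, and nothing says excluded people leave that count. Section 5 says of the enrolment target "this allows for a drop-out rate of just under 10"%, but does not say that this allowance covers image exclusions.

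**Conclusion.** The concern holds in a limited form. The criterion is undefined, can operate only after consent and imaging, and is likely to be related to the outcome through the protocol's own definitions of stages 4 and 5. It can bias the primary prevalence and the stage 4/5 prevalences downward, contrary to the aim of a representative sample.

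The direction rests on impaired participants being excluded at a higher rate than others, which is plausible but not documented. The size is not derivable. Under the stated assumptions a true 10% would be estimated as 5.9-9.0%, or 7.6-9.4% if 40% of impairment lies in eyes that image as well as anyone else's. Precision does not protect against this: with no unimpaired participants lost, excluding a quarter of cases is enough for the expected interval to miss 10%. The change is worth making because the criterion is not needed to measure acuity, and data on people excluded during recruitment may not be recoverable.

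**What to change.** Delete the image-quality item from the exclusion criteria in Section 3.4, and state the following in Sections 2.1 and 5.1:

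- **Denominator:** every consented participant with a measured BCVA.
- **Numerator:** those with BCVA LogMAR ≥ 0.3 in at least one eye attributed to SCR or maculopathy, from images or, where these are ungradable, from the slit-lamp and dilated examination already scheduled.
- **Ungradable images:** record the fact and the cause (for example vitreous haemorrhage, cataract, poor cooperation), and report how often each occurs.
- **Undetermined cause:** put impaired participants whose cause cannot be established in a separate category. With a attributed cases, u undetermined and N in the denominator, report a/N (counted as non-cases) and (a + u)/N (counted as cases).
- **Image-dependent secondary items:** treat these alone as missing.

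The sample size does not change. The cost is a protocol amendment and a small addition to the eCRF for ungradable status, its cause and undetermined attribution. The real downside is that some stages and attributions will rest on examination, which is less sensitive than imaging. The two bounds show how much undetermined cause matters, though they do not correct for disease that the examination misses.
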